More recently, bosutinib was also authorized in adult patients with newly-diagnosed chronic phase (CP) Philadelphia chromosome-positive chronic myelogenous leukaemia (Ph+ CML) (EMA, 2019) based on the results obtained in the BEFORE study (Cortes, 2018a). In this study bosutinib was compared with imatinib in 536 newly diagnosed CML patients in the 'chronic phase'. The main measure of effectiveness was the number of patients who had a 'major molecular response'. After one year of treatment, 47% (116 out of 246) of patients treated with bosutinib had a major molecular response, compared with 37% (89 out of 241) of patients treated with imatinib.

Diarrhea is the most frequent side effect related to bosutinib in clinical trials (80% any grade, <10% of grade 3–4). This side-effect is usually well-managed with dose reductions/interruptions, since <1% of the patients treated with bosutinib in the BEFORE study discontinued treatment due to diarrhea (Cortes, 2012; Cortes, 2018b). In general, pleural effusion is a rare complication in bosutinib treated patients. However, patients who had pleural effusion while on dasatinib and later received bosutinib treatment had a high risk of recurrence of this complication (Gambacorti, 2018). Cardiac and vascular toxicity have been evaluated in bosutinib treated patients enrolled in clinical trials showing a good safety profile. Similar incidences were observed with bosutinib (first or later lines) or comparing to imatinib treated patients (Cortes, 2016). A decrease in the glomerular filtration rate has been observed with long-term exposure to bosutinib. Renal AEs were reported in 73/570 patients (13%) receiving bosutinib as a second-line or later treatment, and in 22/248 (9%) receiving bosutinib as first-line treatment (Cortes, 2017).

6.3 **Overview of Atezolizumab**

Atezolizumab is a monoclonal antibody targeting programmed death ligand 1 (PD-L1 or CD274 antigen). PD-L1 is thought to play an important role in suppressing the immune system triggered by disease, by reducing the proliferation of antigenspecific CD8+ T-cells and controlling the accumulation of foreign antigen-specific T-cells. Up-regulation of PD-L1 has been suggested as a mechanism used by cancer cells to evade the host immune system (Markham, 2016). Atezolizumab has been approved in Europe (EMA, 2019) as monotherapy for the treatment of adult patients with locally advanced or metastatic urothelial carcinoma (UC):

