- b. If corticosteroids have been initiated, they must be tapered over ≥ 1 month to ≤ 10 mg/day oral prednisone or equivalent before atezolizumab can be resumed.
- c. Resumption of atezolizumab may be considered in subjects who are deriving benefit and have fully recovered from the immune-related event. Subjects can be rechallenged with atezolizumab only after approval has been documented by both the investigator (or an appropriate delegate) and the Sponsor

11.6.2.10 *Immune-Related Meningoencephalitis*

Immune-related meningoencephalitis is an identified risk associated with the administration of atezolizumab. Immune-related meningoencephalitis should be suspected in any subject presenting with signs or symptoms suggestive of meningitis or encephalitis, including, but not limited to, headache, neck pain, confusion, seizure, motor or sensory dysfunction, and altered or depressed level of consciousness. Encephalopathy from metabolic or electrolyte imbalances needs to be distinguished from potential meningoencephalitis resulting from infection (bacterial, viral, or fungal) or progression of malignancy, or secondary to a paraneoplastic process. All subjects being considered for meningoencephalitis should be evaluated urgently with a CT scan and/or MRI scan of the brain to evaluate for metastasis, inflammation, or edema. If deemed safe by the treating physician, a lumbar puncture should be performed and a neurologist should be consulted. For specific management guidelines.

11.6.2.11 *Immune-related Nephritis*

Immune-related nephritis is an identified risk associated with the administration of atezolizumab. Immune-related nephritis is a relatively rare complication of checkpoint inhibitor therapy with the most common reported underlying pathology being acute tubulo-interstitial nephritis (ATIN). The most common presentation is asymptomatic increase in creatinine levels. In the absence of alternative etiologies (e.g., prerenal and postrenal causes, and concomitant medications), immune-related nephritis is defined as renal dysfunction requiring steroids treatment and/or confirmed by biopsy. For specific management guidelines, please see Table 12.

Table 12. Management Guidelines for Immune-Related Nephritis

Adverse Event	Management

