12.15.2 Chemistry

Serum chemistry consists of a peripheral blood draw with the following assessments: sodium, potassium, blood urea nitrogen (BUN) or urea, fasting glucose, albumin, creatinine, total cholesterol, triglycerides, total bilirubin (direct and indirect, only if total bilirubin is out normal range), GOT, GPT, GGT, alkaline phosphatase, LDH, magnesium, phosphorous and calcium. Amylase and lipase determinations will be added only in screening and during bosutinib plus atezolizumab combination treatment.

The chemistry assessments must be obtained at:

- Screening
- During first therapy (before treatment):
 - Day 1 of cycle 1 (visit 1/D1).
- During second therapy (before treatment):
 - Day 1 of cycle 2. Before the patient takes the bosutinib plus atezolizumab combination for first time.
 - Day 1 of cycles 4, 7, 10, and 13.

- During third therapy:
 - Day 1 of cycle 14. Before the patient takes bosutinib 400 mg/day in monotherapy, for the first time again for the treatment of CML.
 - Day 1 of cycle 20.
 - At the End of Treatment: Day 29 (Last dose) of cycle 25.
 - At the End of Study, (visit EOS or follow up): 28 days after the last dose.

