15.3.3 Laboratory Abnormalities

For laboratory tests covered by the Common Terminology Criteria for Adverse Events (CTCAE) version 5.0 the study's biostatistician and reporting team will grade laboratory data accordingly. For laboratory tests covered by CTCAE, a Grade 0 will be assigned to all non-missing values not graded as 1 or higher. Grade 5 will not be used.

In some cases, (e.g., white blood cell differentials) the lower limits of normal ranges used in CTCAE definition have to be replaced by a clinically meaningful limit expressed in absolute counts.

For laboratory tests where grades are not defined by CTCAE, results will be graded by the low/normal/high classifications based on laboratory normal ranges.

The following by-safety subset summaries will be generated separately for hematology, and biochemistry tests:

- number and percentage of patients with clinically significant laboratory abnormalities, by parameter and worst post-baseline CTCAE grade. Each patient will be counted only for the worst grade observed post-baseline, regardless of the baseline status
- shift tables using CTCAE grades to compare baseline to the worst on-treatment value

- for laboratory tests where CTCAE grades are not defined, shift tables using the low/normal/high
- classification to compare baseline to the worst on-treatment value.
- listing of all laboratory data with values flagged to show the corresponding CTCAE grades and the classifications relative to the laboratory normal ranges.

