6.9. Safety data analysis

Reporting of safety information will be split into subsets by first phase, second phase, third phase, and fourth phase.

Adverse Events: Summary tables for adverse events (AEs) have to include only AEs that started or worsened during the on-treatment period, the treatment-emergent AEs (TEAEs). However, all safety data (including those from the pre-treatment period) will be listed and those collected during the pre-treatment period are to be flagged.

The incidence of treatment-emergent adverse events (new or worsening from baseline) will be summarized by system organ class and/or preferred term, severity (based on CTCAE grades), type of adverse event, causality relation to study treatment by the phases or subsets previously described.

Deaths reportable as SAEs and non-fatal serious adverse events will be listed by patient and tabulated by type of adverse event and safety subset.

Specific safety event categories will be considered. Such categories consist of one or more well-defined safety events which are similar in nature and for which there is a specific clinical interest in connection with the study treatment(s).

For each specified safety event category, number, and percentage of patients with at least one event part of the safety set will be reported. Also, AESI will be summarized and analyzed.

Laboratory abnormalities: For laboratory tests covered by the Common Terminology Criteria for Adverse Events (CTCAE) version 5.0 the study's biostatistician and reporting team will grade laboratory data accordingly. For laboratory tests covered by CTCAE, a Grade 0 will be assigned to all non-missing values not graded as 1 or higher. Grade 5 will not be used.

In some cases, (e.g., white blood cell differentials) the lower limits of normal ranges used in CTCAE definition have to be replaced by a clinically meaningful limit expressed in absolute counts.

For laboratory tests where grades are not defined by CTCAE, results will be graded by the low/normal/high classifications based on laboratory normal ranges.

The following by-safety subset summaries will be generated separately for hematology, and biochemistry tests:

- number and percentage of patients with clinically significant laboratory abnormalities, by parameter and worst post-baseline CTCAE grade. Each patient will be counted only for the worst grade observed post-baseline, regardless of the baseline status

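### The protocol names falling GFR as a long-term bosutinib effect, but no planned summary measures it, and a decline that stays within creatinine Grade 0 shows as no change in the shift table

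*SAP*

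**What the plan says.** **The risk.** Protocol 6.2: "A decrease in the glomerular filtration rate has been observed with long-term exposure to bosutinib". It gives no size or timing for the fall. It does give renal adverse event rates, including "22/248 (9%) receiving bosutinib as first-line treatment". On immune-related nephritis, which Protocol 11.6.2.11 calls an identified atezolizumab risk: "The most common presentation is asymptomatic increase in creatinine levels".

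**The data.** The chemistry panel in Protocol 12.15.2 includes "sodium, potassium, blood urea nitrogen (BUN) or urea, fasting glucose, albumin, creatinine, total cholesterol, triglycerides". It is drawn at screening, on day 1 of cycles 1, 2, 4, 7, 10, 13, 14 and 20, at end of treatment and at end of study. Protocol 12.5 records age and gender.

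**The analysis.** SAP 6.9 and Protocol 15.3.3 plan three kinds of laboratory output:

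- a count of patients with clinically significant abnormalities by worst CTCAE grade, where "Each patient will be counted only for the worst grade observed post-baseline, regardless of the baseline status";
- tables that cross-classify each patient's baseline grade against the worst grade reached on treatment;
- a flagged listing of all values.

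Any non-missing value below Grade 1 is assigned Grade 0. The synopsis (Safety Evaluation) adds descriptive statistics over time, limited to clinically significant laboratory changes. Neither document mentions eGFR or creatinine clearance as something to derive or analyse.

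**The concern.** Safety is the primary objective, and the protocol itself names a gradual loss of kidney function as a known effect of one study drug. A symptomless creatinine rise is also the usual first sign of a known effect of the other. The planned summaries work on grades. A grade tied to the upper limit of normal says little about a patient who starts low in the normal range and drifts towards its top, although GFR may have fallen appreciably. The study could then describe the renal safety of the combination without any table showing how far renal function moved, although the data to show it are collected throughout.

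**Working it through.** **1. The plan's own renal figures.** 73/570 = 12.8% (stated as 13%) and 22/248 = 8.9% (stated as 9%); both reproduce. Applied to 36 patients, the first-line rate gives 36 x 22/248 = 3.2 patients with a recognised renal event. This counts recognised events only and says nothing about how many declines go untabulated.

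**2. Exposure.** Protocol 11.5: 4 + 48 + 48 = 100 weeks of bosutinib, of which the middle 48 weeks are in combination with atezolizumab.

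**3. What the tables can show.** If baseline and worst on-treatment creatinine are both Grade 0, the shift table records 0-to-0 and the worst-grade table records no abnormality. The size of the change is then visible only in the listing.

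**4. How large such a change can be.** The documents print no CTCAE creatinine cut-offs (Protocol Appendix B gives a link), no ULN and no eGFR equation. The following are therefore assumptions:

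- CKD-EPI 2021: eGFR = 142 x min(s/k, 1)^a x max(s/k, 1)^-1.2 x 0.9938^age (x 1.012 for women), where s is creatinine in mg/dL, with k = 0.9 and a = -0.302 for men, and k = 0.7 and a = -0.241 for women;
- ULN 1.2-1.3 mg/dL for men and 1.0-1.1 for women;
- Grade 1 above the ULN, Grade 2 above 1.5 x baseline.

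The highest creatinine that stays Grade 0 is then s1 = min(ULN, 1.5 x s0), where s0 is baseline. The percentage loss is 1 - eGFR(s1)/eGFR(s0), and age cancels.

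Worked cases at age 55:

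- Woman, 0.7 to 1.0 mg/dL (1.43-fold): eGFR 102 to 67. Loss = 1 - (1.0/0.7)^-1.2 = 34.8%. Grade 0.
- Man, 0.8 to 1.2 mg/dL: eGFR 105 to 71. Loss = 1 - (1.2/0.9)^-1.2 / (0.8/0.9)^-0.302 = 31.7%. With ULN 1.2 this sits exactly on both boundaries (the ULN and 1.5-fold), so any further rise is graded.

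Largest loss that stays Grade 0:

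| Men, baseline mg/dL | ULN 1.2 | ULN 1.3 |
|---|---|---|
| 0.6 | 11.5% | 11.5% |
| 0.7 | 23.0% | 23.0% |
| 0.8 | 31.7% | 31.7% |
| 0.9 | 29.2% | 35.7% |
| 1.0 | 19.7% | 27.0% |
| 1.1 | 9.9% | 18.2% |

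| Women, baseline mg/dL | ULN 1.0 | ULN 1.1 |
|---|---|---|
| 0.5 | 15.1% | 15.1% |
| 0.6 | 28.7% | 28.7% |
| 0.7 | 34.8% | 38.5% |
| 0.8 | 23.5% | 31.8% |
| 0.9 | 11.9% | 21.4% |

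The range is about 10% to 39%. A full one-third loss stays Grade 0 in three of these 22 cells: men at 0.9 with ULN 1.3, and women at 0.7 with either ULN.

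**5. Dependence on the equation.** A one-third loss needs a 1.42-fold creatinine rise under MDRD and a 1.50-fold rise under Cockcroft-Gault. Under those equations it stays Grade 0 over a wider band of baselines (for example, men at 0.7 and 0.8 and women at 0.5 and 0.6).

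**The case against.** The strongest reply is that the plan has several routes to a renal signal and is coherent for a 36-patient exploratory single-arm study. A reader might infer from the worst-grade sentence that renal function is analysed by that table alone. It is not: shift tables against baseline and a listing of every value follow directly. BUN or urea is also measured. Under Protocol 13.2, a result becomes an adverse event if it prompts further testing or a dosing change, or if the investigator or sponsor judges it significant. Protocol 13.9.1 makes both a creatinine rise and nephritis events of special interest. The synopsis and SAP 6.5 also have general wording on descriptive statistics for continuous variables, under which mean creatinine could be shown.

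All of that stands, and it rules out any statement that renal decline would go unreported. It does not supply the missing summary. Shift tables use grades. The bosutinib renal event of special interest depends on the investigator judging the creatinine rise clinically significant. Protocol 11.6.2.11 defines immune-related nephritis by steroid treatment or biopsy. The SAP's own list of special-interest events has vascular items and a catch-all, with no renal item. A mean creatinine can conceal individual losses.

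It is also fair that the documents give no size for the expected GFR fall, and that a single arm cannot separate atezolizumab from the bosutinib effect already acknowledged. The second point limits interpretation; it does not remove the value of describing the change.

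**Conclusion.** The point holds as a gap in the summaries: GFR decline is named as a risk, the inputs to estimate it are collected, and no planned table quantifies it. A decline within Grade 0 would be visible only in the listing.

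The size is conditional. On the stated equation, ULNs and grade cut-offs, none of which are in the documents, the largest loss that stays Grade 0 is about 10% to 39%.

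Three stronger readings should be avoided. A one-third loss is not generally graded 0: at most tested baselines it would reach Grade 1 or 2. The combination is not given for two years; it is given for 48 weeks within about 100 weeks of bosutinib. The 9% first-line renal event rate gives no basis for estimating how many patients would have an untabulated decline.

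This is a low-cost improvement to the description of the primary endpoint, not the correction of an invalid analysis.

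**What to change.** In SAP 6.9, with matching text in Protocol 15.3.3:

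- Derive eGFR from creatinine, age and sex at every chemistry visit, using one named equation.
- Report change by visit from the pre-bosutinib value (stating whether that is the screening or the cycle 1 day 1 sample) and from the cycle 2 day 1 pre-atezolizumab value.
- Report the number of patients with a prespecified percentage fall (for example, 30% or more) and with eGFR below a prespecified level (for example, 60), each with an exact 95% confidence interval, the method SAP 6.5 already uses for proportions.
- Label these as descriptive reporting thresholds, not management rules.
- State that without a comparator the change cannot be attributed to atezolizumab rather than bosutinib.

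The cost is a few lines of text, one derived variable and one added summary table. No new samples or visits are needed.

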13.9.1 Adverse Event of Special Interest

AESIs require ongoing monitoring by investigators and rapid identification and communication by the investigator to the sponsor. All AESIs, whether they are SAEs or not, must be reported immediately (within 24 hours) to the sponsor. The sponsor has determined that the events listed below (whether considered serious or non-serious by investigators) should be considered AESIs, and should therefore be reported within 24 hours:

- 1) In relation to bosutinib:
 - A. Grade 3-4 diarrhea
 - B. Grade 3-4 nausea and vomiting
 - C. Potential drug-induced liver injury showed by abnormal values in liver enzyme (ALT increased and AST increased) concurrent with abnormal elevation in total bilirubin that meet the criteria outlined below:
 - a. Patients with AST or ALT and total bilirubin baseline values within the normal range who subsequently present with AST or ALT ≥ 3 times the upper limit of normal concurrent with a total bilirubin $\geq 2 \times$ ULN with no evidence of hemolysis and an alkaline phosphatase $\leq 2 \times$ ULN or not available;
 - b. For patients with preexisting ALT or AST or total bilirubin values above the upper limit of normal, the following threshold values should be used:
 - i. For patients with pre-existing AST or ALT baseline values above the normal range: AST or ALT ≥ 2 times the baseline values and $\geq 3 \times$ ULN, or $\geq 8 \times$ ULN (whichever is smaller).
 - ii. For patients with pre-existing values of total bilirubin above the normal range: Total bilirubin increased by one time the upper limit of normal or ≥ 3 times the upper limit of normal (whichever is smaller).

D. Myelosuppression (Anemia, Neutropenia, Leukopenia) considered clinically significant by the investigator.

E. Hemorrhage considered clinically significant by the investigator

F. Infection

G. Skin disorders (Rash) considered clinically significant by the investigator

H. Clinically significant immunological events (Hypersensitivity)

I. Renal dysfunction (increased blood creatinine considered clinically significant by the investigator)

J. Pleural effusions

K. Clinically significant cardiac events (QT prolongation, atrial fibrillation, sinus bradycardia, tachycardia, supraventricular tachycardia, bradycardia, premature ventricular contractions, pericardial effusion, right bundle branch block, sinus tachycardia, or premature atrial contractions).

2) In relation to atezolizumab:

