15.3.2 Adverse Events

Summary tables for adverse events (AEs) have to include only AEs that started or worsened during the on-treatment period, the treatment-emergent AEs (TEAEs). However, all safety data (including those from the pre-treatment period) will be listed and those collected during the pre-treatment period are to be flagged.

The incidence of treatment-emergent adverse events (new or worsening from baseline) will be summarized by system organ class and/or preferred term, severity (based on CTCAE grades), type of adverse event, causality relation to study treatment by the phases or subsets previously described.

Deaths reportable as SAEs and non-fatal serious adverse events will be listed by patient and tabulated by type of adverse event and safety subset.

Specific safety event categories will be considered. Such categories consist of one or more well-defined safety events which are similar in nature and for which there is a specific clinical interest in connection with the study treatment(s).

For each specified safety event category, number and percentage of patients with at least one event part of the safety set will be reported. Also AESI will be summarized and analyzed.

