- shift tables using CTCAE grades to compare baseline to the worst on-treatment value
- for laboratory tests where CTCAE grades are not defined, shift tables using the low/normal/high
- classification to compare baseline to the worst on-treatment value.
- listing of all laboratory data with values flagged to show the corresponding CTCAE grades and the classifications relative to the laboratory normal ranges.

Other Safety Data: other safety data collected (e.g., ECG, vital signs) will be listed and summarized using descriptive statistics as appropriate. Notable values will be flagged. Notable/Abnormal values for safety data will be further specified in the RAP.

The list of safety data will be summarized as:

Variables	Data
Laboratory (hematology, biochemistry, urinary and others), Vital signs, changes in physical exam findings and Electrocardiogram abnormalities	Number and percentage Description (mapped to MedDRA thesaurus terms) Time of appearance in relation to study's drug administration/data of onset (n-TEAE or TEAE, days/hours) End date or ongoing until recovery or stability Severity-CTCAE grades (from 0 to 5 or low/normal/high for laboratory tests or according to study protocol) Seriousness (according to definitions of study protocol) SAE (yes or not) Causality (Definitely Not Related, Probably Not Related, Possibly Related, Probably Related or Definitely Related) Expectedness (according to Clinical Investigator's Brochure) Outcome/evolution Any medication used to treat the AE or concomitant medication (yes or not, an specify active substance name, dose, and frequency) If it requires further exams/test(yes or not, an specify)
Hypersensitivity	
Adverse Event of Special Interests (AESI): 1. Myocardial infarction 2. Angina 3. Coronary artery disease 4. Cerebrovascular ischemic disease 5. New onset or worsening of peripheral artery occlusive disease 6. Retinal vascular thrombosis, both venous and arterial. 7. Venous thromboembolism that could result in significant compromise of organ function or other significant consequences 8. Any other event considered important by the investigator	
Pregnancy	

All variables will be recorded, ongoing or starting within 28 days after end of treatment/patient decision to discontinue treatment (pos-treatment).

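### The AESI list in SAP 6.9 names none of the 21 AESI entries fixed in protocol 13.9.1, so the planned AESI summary would not report the protocol's AESIs as such

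*SAP*

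**What the plan says.** Protocol 13.9.1 sets the AESI list with the sponsor's authority: "The sponsor has determined that the events listed below (whether considered serious or non-serious by investigators) should be considered AESIs". Eleven lettered entries follow for bosutinib (A to K) and ten for atezolizumab (A to J). The same section attaches a reporting duty: "All AESIs, whether they are SAEs or not, must be reported immediately (within 24 hours) to the sponsor".

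The table of safety data at the end of SAP 6.9 has a row that begins "Adverse Event of Special Interests (AESI): 1. Myocardial infarction 2. Angina 3. Coronary artery disease 4. Cerebrovascular ischemic disease". The row goes on to peripheral arterial occlusive disease, retinal vascular thrombosis and venous thromboembolism. An eighth item admits whatever else the investigator thinks important. Hypersensitivity has its own row in that table, outside the AESI list.

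Both documents promise an AESI analysis. Protocol 15.3.2 says "Also AESI will be summarized and analyzed" and SAP 6.9 says "Also, AESI will be summarized and analyzed". SAP 6.9 also promises a count by category: "For each specified safety event category, number, and percentage of patients with at least one event part of the safety set will be reported". Protocol 15.3.2 has nearly the same sentence. Neither document names a category. The SAP defers to a further document for one matter only: "Notable/Abnormal values for safety data will be further specified in the RAP".

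**The concern.** The primary objective is the safety profile of the combination, and SAP 6.4 sends the reader to 6.9 for how safety is analysed. That section therefore puts the primary objective into practice. A programmer who builds the AESI table from the list there would tabulate infarction, angina, stroke-type events and thrombosis. Nephritis, vasculitis, severe skin reactions, drug-induced liver injury and the other events that the sponsor singled out would not be shown as AESIs. Atezolizumab is the drug being added to bosutinib, and no atezolizumab entry is named in the SAP list. If the choice of list is left until the data are in, which safety events are highlighted becomes a post hoc decision.

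**Working it through.** No sample size, power or error rate depends on this point. The check is a count and a side-by-side reading of the two lists.

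**Step 1: count the entries.** Protocol 13.9.1: bosutinib A to K = 11, atezolizumab A to J = 10, and 11 + 10 = 21. SAP 6.9: 7 named items + 1 open item = 8.

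**Step 2: look for each SAP item in 13.9.1.**

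| SAP 6.9 item | Named in 13.9.1? | Could it fall under an open class? |
|---|---|---|
| 1 Myocardial infarction | No | Atezolizumab G (cardiac, grade 2 or higher, examples only) |
| 2 Angina | No | Atezolizumab G |
| 3 Coronary artery disease | No | Atezolizumab G |
| 4 Cerebrovascular ischemia | No | None |
| 5 Peripheral arterial occlusion | No | None |
| 6 Retinal vascular thrombosis | No | Atezolizumab F (ocular, examples only) |
| 7 Venous thromboembolism | No | None |

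Named in both lists: 0 of 7. Possibly covered: items 1, 2, 3 and 6 = 4. In no protocol entry: items 4, 5 and 7 = 3. Check: 4 + 3 = 7. A word comparison of the lists found only generic words in common, such as those for significance and for the investigator.

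**Step 3: read it the other way.** The seven items can touch atezolizumab F and G. On a loose reading they also touch bosutinib K, whose bracketed terms are rhythm, conduction and pericardial events. That leaves 21 − 3 = 18 protocol entries with no counterpart among the seven. Hypersensitivity (bosutinib H, part of atezolizumab D) is summarized in its own SAP row, but not as an AESI.

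**Step 4: ask whether other tables supply the missing counts.** For an entry that bundles terms, the number of patients affected is not the sum of the preferred-term rows, because one patient can have several terms. Bosutinib D is an example: "Myelosuppression (Anemia, Neutropenia, Leukopenia) considered clinically significant by the investigator" names 3 terms. Bosutinib K names 11. Liver injury (bosutinib C, atezolizumab A) needs concurrent findings and is defined differently for each drug. Entries that name two or more events or need concurrent findings are bosutinib B, C, D and K (4) and atezolizumab A, D, F, G and J (5). That is at least 4 + 5 = 9 of 21. For these, a patient count needs a stated category.

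**Step 5: look for named categories.** The number of safety event categories named as such is 0 in SAP 6.9 and 0 in protocol 15.3.2.

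**The case against.** The best defence is that the SAP sentence on AESIs does not itself limit the summary to the seven items. Investigators must report every 13.9.1 event as an AESI, several protocol entries already turn on clinical significance in the investigator's view, and the SAP's eighth item is open to investigator judgment. The protocol AESIs could therefore reach the summary by that route. This makes the consequence likely rather than certain. It does not repair the text, because an item that depends on each investigator's opinion cannot reproduce a list that the sponsor fixed in advance.

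A second defence is that the seven items may be the vascular occlusive events whose incidence the protocol synopsis promises. That is plausible. But both documents only expand the abbreviation VOE, neither defines the set, and SAP 6.9 labels the items AESI.

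A third is that the study is exploratory and descriptive and the events appear elsewhere. That stands, and it limits the size of the point.

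Three stronger readings are tempting, and the documents do not support them:

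- *Protocol AESIs would go unreported.* They would still appear in the treatment-emergent event tables, laboratory tables and listings. Hypersensitivity has its own row.
- *The SAP created the gap in the categories.* The unnamed categories are carried over from protocol 15.3.2.
- *The four reporting phases in SAP 6.9 are also wrong and should become three.* Protocol 15.3.1 itself prescribes four. They match Group 1's four treatment steps in the synopsis and section 11.5: bosutinib alone, the combination at 840 mg every two weeks, the combination at 1680 mg every four weeks, and bosutinib alone. Three periods would pool Group 1's two combination steps.

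**Conclusion.** SAP 6.9 is wrong as written on this point. The list it labels AESI shares no named item with the 21 entries in protocol 13.9.1. Four of its seven items have a possible home in an open protocol class, three have none, and no text explains the difference. The AESI summary promised for the primary safety objective would not report the protocol-defined AESIs as such. The effect is confined to that summary. The secondary gap, that neither document names its safety event categories, is missing detail and no more.

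The conclusion assumes that the analyst follows the list in SAP 6.9. It also assumes that the RAP, which is not among the documents, does only what the SAP assigns to it, namely define notable and abnormal values.

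**What to change.** In SAP 6.9, replace the AESI list with the entries of protocol 13.9.1, split by drug. For each entry, give the count and percentage of patients with one or more events, with the exact binomial 95% interval already set out in SAP 6.5. Keep the seven vascular items as a separately labelled category, and state whether they are the VOE set that the synopsis promises to report.

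The 13.9.1 entries can also serve as the unnamed safety event categories, which would close the secondary gap in the SAP. The four reporting phases can stay as they are.

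The cost is SAP wording only. The protocol already requires these events to be reported as AESIs, and the SAP already promises the summary, the category counts and the intervals. No data collection changes.
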